10.12 PUBLICATIONS

Publication by the clinical trial site(s) of any data from this study must be carried out in accordance with the Clinical Trial Agreement.


APPENDICES**Appendix 1: Known CYP3A or CYP2C8 Substrates**

Note: Drugs or foods that are substrates for CYP3A should be used only if medically necessary and therapeutic alternatives are not available. Medications that are metabolized via CYP2C8 may be used as medically indicated but with caution.

The following lists provide known sensitive CYP3A substrates, CYP3A substrates with a narrow therapeutic range, and CYP2C8 substrates.

Additional information can be found at

<http://www.medicine.iupui.edu/clinpharm/ddis/ClinicalTable.asp> and

<http://www.pharmacytimes.com/issue/pharmacy/2008/2008-09/2008-09-8687>.

Sensitive CYP3A Substrates	
budesonide buspirone eplerenone eletriptan felodipine fluticasone lovastatin	midazolam saquinavir sildenafil simvastatin triazolam vardenafil
CYP3A Substrates with a Narrow Therapeutic Range	
alfentanil astemizole cisapride cyclosporine diergotamine ergotamine	fentanyl pimozide quinidine sirolimus tacrolimus terfenadine
CYP2C8 Substrates	
paclitaxel torsemide amodiaquine	cervistatin repaglinide rosiglitazone pioglitazone

Appendix 2: Medications or Foods Known to Inhibit or Induce CYP3A

Note: Subjects receiving IPI-145 are prohibited from concomitant use of medications or foods that are known to be strong inhibitors or inducers of CYP3A.

The following list provides medications known to induce or inhibit CYP3A activity. Note that this is not a comprehensive list of all medications which may modulate CYP3A activity.

Additional information can be found at

- <http://www.fda.gov/Drugs/DevelopmentApprovalProcess/DevelopmentResources/DrugInteractionsLabeling/ucm080499.htm>

Classification of In Vivo Inhibitors of CYP3A

Strong Inhibitors⁽¹⁾	Moderate inhibitors⁽²⁾	Weak inhibitors⁽³⁾
Boceprevir, clarithromycin, conivaptan, grapefruit juice, ⁽⁵⁾ indinavir, itraconazole, ketoconazole, lopinavir/ritonavir, mibepradil, ⁽⁶⁾ nefazodone, neflifavir, posaconazole, ritonavir, saquinavir, telaprevir, telithromycin, voriconazole	Amprenavir, aprepitant, atazanavir, ciprofloxacin, darunavir/ritonavir, diltiazem, erythromycin, fluconazole, fosamprenavir, grapefruit juice, ⁽⁵⁾ imatinib, verapamil	Alprazolam, amiodarone, amlodipine, atorvastatin, bicalutamide, cilostazol, cimetidine, cyclosporine, fluoxetine, fluvoxamine, ginkgo, ⁽⁴⁾ goldenseal, ⁽⁴⁾ isoniazid, nilotinib, oral contraceptives, ranitidine, ranolazine, tipranavir/ritonavir, zileuton

1. A strong inhibitor for a specific CYP is defined as an inhibitor that increases the AUC of a substrate for that CYP by equal or more than 5-fold or >80% decrease in CL.
2. A moderate inhibitor for a specific CYP is defined as an inhibitor that increases the AUC of a sensitive substrate for that CYP by less than 5-fold but equal to or more than 2-fold or 50-80% decrease in CL.
3. A weak inhibitor for a specific CYP is defined as an inhibitor that increases the AUC of a sensitive substrate for that CYP by less than 2-fold but equal to or more than 5-fold or 20-50% decrease in CL.
4. Herbal product.
5. The effect of grapefruit juice varies widely among brands and is concentration-, dose-, and preparation-dependent. Studies have shown that it can be classified as a “strong CYP3A inhibitor” when a certain preparation was used (e.g., high dose, double strength) or as a “moderate CYP3A inhibitor” when another preparation was used (e.g., low dose, single strength).
6. Withdrawn from the United States market because of safety reasons.

Classification of In Vivo Inducers of CYP3A

Strong Inducers ≥ 80% decrease in AUC	Moderate Inducers 50-80% decrease in AUC	Weak Inducers 20-50% decrease in AUC
Avasimibe, ⁽¹⁾ carbamazepine, phenytoin, rifampin, St. John's wort ⁽²⁾	Bosentan, efavirenz, etravirine, modafinil, naftillin	Amprenavir, aprepitant, armodafinil, echinacea, ⁽³⁾ pioglitazone, prednisone, rufinamide

1. Not a marketed drug.
2. The effect of St. John's wort varies widely and is preparation-dependent.
3. Herbal product.

Appendix 3: P-gp Substrates and Medications that are Inhibitors of P-gp

Note: In subjects receiving IPI-145, caution should be used for the concomitant use of P-gp substrates or inhibitors

The following list provides medications that are substrates or inhibitors of P-gp. Note that this is not a comprehensive list of all medications which may be substrates of P-gp or may modulate P-gp activity.

P-gp Substrates	
Amitriptyline	Loperamide
Amiodarone	Losartan
Atorvastatin	Lovastatin
Cefoperazone	Methadone
Chlorpromazine	Methotrexate
Cimetidine	Methylprednisolone
Ciprofloxacin	Morphine
Clarithromycin	Nadolol
Colchicine	Norfloxacin
Cyclosporine	Nortriptyline
Dexamethasone	Ondansetron
Digoxin	Omeprazole
Diltiazem	Pantoprazole
Erythromycin	Phenytoin
Estradiol	Pravastatin
Fentanyl	Propranolol
Fexofenadine	Quinidine
Hydrocortisone	Ranitidine
Itraconazole	Sirolimus
Lansoprazole	Tacrolimus
Levofloxacin	Timolol
Lidocaine	Trimethoprim
	Verapamil

P-gp Inhibitors	
Amiodarone	Ketoconazole
Amitriptyline	Lovastatin
Carvedilol	Mefloquine
Chlorpromazine	Nicardipine
Clarithromycin	Nifedipine
Cortisol	Ofloxacin
Cyclosporine	Omeprazole
Desipramine	Pantoprazole
Diltiazem	Progesterone
Dipyridamole	Propafenone
Doxepin	Propranolol
Erythromycin	Quinidine
Felodipine	Rifampicin (Rifampin)
Fluphenazine	Saquinavir
Grapefruit juice	Simvastatin
Haloperidol	Sirolimus
Itraconazole	Tacrolimus
	Testosterone
	Verapamil

Source: Atkinson AJ et al. Principles of Clinical Pharmacology, 2nd ed. Academic Press, Massachusetts, 2007.

Appendix 4: ECOG Performance Status

Grade	ECOG
0	Fully active, able to carry on all pre-disease performance without restriction
1	Restricted in physically strenuous activity but ambulatory and able to carry out work of a light or sedentary nature, e.g., light house work, office work
2	Ambulatory and capable of all self-care but unable to carry out any work activities. Up and about more than 50% of waking hours
3	Capable of only limited self-care, confined to bed or chair more than 50% of waking hours
4	Completely disabled. Cannot carry on any self-care. Totally confined to bed or chair
5	Dead

Source : Eastern Cooperative Oncology Group : http://www.ecog.org/general/perf_stat.html

As published in Am. J. Clin. Oncol.:

Appendix 5: Examples of Suitable Prior Chemotherapy

1. Bendamustine
2. Cyclophosphamide
3. Ifosfamide
4. Chlorambucil
5. Melphalan
6. Busulfan
7. Nitrosoureas
8. Fludarabine

Please contact the Medical Monitor regarding the appropriateness of any prior chemotherapy not listed above prior to subject enrollment.

Appendix 6: QoL Instrument - EQ-5D Questionnaire**(English version for the US)**

By placing a checkmark in one box in each group below, please indicate which statements best describe your own health state today.

Mobility

I have no problems in walking about	
I have some problems in walking about	
I am confined to bed	

Self-Care

I have no problems with self-care	
I have some problems washing or dressing myself	
I am unable to wash or dress myself	

Usual Activities (eg., work, study, housework, family or leisure activities)

I have no problems with performing my usual activities	
I have some problems with performing my usual activities	
I am unable to perform my usual activities	

Pain/Discomfort

I have no pain or discomfort	
I have moderate pain or discomfort	
I have extreme pain or discomfort	

Anxiety/Depression

I am not anxious or depressed	
I am moderately anxious or depressed	
I am extremely anxious or depressed	

To help people say how good or bad a health state is, we have drawn a scale (rather like a thermometer) on which the best state you can imagine is marked 100 and the worst state you can imagine is marked 0.

We would like you to indicate on this scale how good or bad your own health is today, in your opinion. Please do this by drawing a line from the box below to whichever point on the scale indicates how good or bad your health state is today.

Your own
health state
today.

ULN	Upper Limit Of Normal
UNK	Unknown
WBC	White Blood Cell
WHO	World Health Organization

1 INTRODUCTION

The purpose of this Statistical Analysis Plan (SAP) is to provide a detailed description of the statistical methods to be implemented for the analysis of the data collected in the IPI-145-06 study: *A Phase 2 Study of IPI-145 in Subjects with Refractory Indolent Non-Hodgkin Lymphoma* (iNHL).

This SAP is based on protocol amendment 3 (global), dated 03 Nov 2015.

2 STUDY OBJECTIVES

2.1 PRIMARY OBJECTIVE

The primary objective of this study is to evaluate the antitumor activity of IPI-145 administered to subjects diagnosed with iNHL (defined as follicular lymphoma [FL], marginal zone lymphoma [MZL; splenic, nodal and extranodal], or small lymphocytic lymphoma [SLL]) whose disease is refractory to rituximab and to either chemotherapy or radioimmunotherapy (RIT).

2.2 SECONDARY OBJECTIVES

The secondary objectives of the study are:

- To evaluate the safety of IPI-145 in all subjects
- To evaluate additional efficacy parameters in all subjects
- To evaluate the PK of IPI-145 and, if applicable, its metabolite(s)

2.3 EXPLORATORY OBJECTIVES

The exploratory objectives of the study are:

- To evaluate whether baseline values or treatment-related changes in biomarkers correlate with IPI-145 clinical activity, safety and/or resistance in iNHL.
- To evaluate whether tumor genomic or pharmacogenomic markers correlate with IPI-145 clinical activity, safety, PK and/or resistance in iNHL
- To evaluate the health-related quality of life (QoL) of subjects

3 STUDY DESIGN

3.1 OVERVIEW

Study IPI-145-06 is a Phase 2, open-label, single arm efficacy and safety study of IPI-145 administered orally to subjects diagnosed with iNHL (FL, MZL or SLL) whose disease is refractory to rituximab and to either chemotherapy or RIT. The study population consists of adult male and female subjects who meet the inclusion/exclusion criteria, enrolled at up to approximately 100 sites worldwide.

All subjects enrolled will be assigned to the same treatment of 25 mg IPI-145 orally twice daily (BID) administered continuously in 28-day treatment cycles for up to 13 cycles. To receive additional cycles of IPI-145 beyond 13 cycles, subjects must have documented evidence of response (CR or PR) or stable disease (SD) at the Cycle 14 Day 1 response assessment according to the revised International Working Group (IWG) criteria. These subjects may continue to receive IPI-145 treatment until disease progression or unacceptable toxicity.

All subjects who permanently discontinue treatment with IPI-145 for reasons other than withdrawal of consent from overall study participation will enter survival follow-up. Survival follow-up will occur every 6 months (± 4 weeks) from permanently discontinuing IPI-145 treatment for up to 3 years after first dose of IPI-145 or until death.

3.2 SAMPLE SIZE CONSIDERATION

The primary endpoint of the study is overall response rate (ORR), as defined in [Section 5.1](#). This study will test the null hypothesis that the ORR is $\leq 30\%$ against the alternative that ORR is $\geq 45\%$. Using a group sequential design with 1 interim analysis, 120 subjects will provide $>90\%$ power to achieve a one-sided overall significance level of 0.025. The interim analysis will occur approximately 4 months after at least 30 subjects (25% of the total) have initiated treatment with IPI-145. The cumulative Type II error to be spent at the interim and final analyses are 0.02 and 0.1, respectively. The interim analysis is intended for futility only and hence no Type I error will be spent.

Among the 120 subjects to be enrolled, approximately 80 will be FL.

3.3 UNBLINDING

Not applicable. This is a single arm open label study.

3.4 INTERIM ANALYSIS

An interim futility analysis will be performed approximately 4 months after at least 30 subjects (25% of total) have initiated treatment with IPI-145. The futility boundary is

non-binding, meaning that the Type I error will be properly controlled if the study continues after the futility boundary is crossed at the interim analysis. If the interim analysis occurs 4 months after exactly 30 subjects have initiated treatment, the one-sided p-value for futility is 0.6552. This is equivalent to a response rate of 26.4% or 7 responders or less out of the 30 subjects. Actual p-value boundary for futility will be calculated based on the number of subjects at the interim analysis by linear interpolation.

ORR based on the Investigator's assessment will be used for the interim analysis.

If the required total number of subjects are accrued for the interim analysis but follow-up is not sufficiently mature to reasonably assess the ORR, accrual may proceed while the data on interim analysis subjects are being collated.

The following data will be reviewed by an external Independent Data Monitoring Committee (IDMC) at the interim analysis: ORR, time to response (TTR), disposition, demographics and baseline characteristics, prior anticancer therapy, medical history, concomitant medications, exposure, dose modifications, treatment-emergent adverse events (TEAEs), serious adverse events (SAEs), deaths, laboratory parameters, and additional data requested by the IDMC. Further details will be provided in the IDMC charter.

4 ANALYSIS SETS

4.1 FULL ANALYSIS SET

The Full Analysis Set (FAS) will include all subjects who have been treated with at least one dose of IPI-145. The FAS will be the primary analysis set for all efficacy and safety analyses.

4.2 EVALUABLE ANALYSIS SET

The Evaluable Analysis Set (EAS) will include all subjects who meet the following criteria:

- Remain in the treatment phase of the study for at least 8 weeks or have a documented disease progression per revised IWG criteria before 8 weeks of treatment
- Have an adequate baseline tumor assessment (at least one nodal target lesion ≥ 1.5 cm in the longest diameter)
- Have at least 1 adequate post baseline tumor assessment unless death due to disease progression
- No major protocol deviations that could have an impact on efficacy (The following list is phrased in terms of deviations. Subjects meeting these conditions will be excluded from the EAS):
 - Have not been diagnosed with indolent NHL [FL, MZL or SLL] (inclusion criterion #2)
 - Do not have disease that is refractory to a chemotherapy induction regimen or RIT (inclusion criterion #3)
 - Do not have disease that is refractory to rituximab (inclusion criterion #4)
 - Prior treatment with any PI3K inhibitor or Bruton's Tyrosine Kinase (BTK) inhibitor (exclusion criterion #2)
 - Grade 3B FL and/or clinical evidence of transformation to a more aggressive subtype of lymphoma (exclusion criterion #7)
 - Have been taking other anticancer therapies during the treatment phase of the study that could seriously confound the effects of the study treatment

The EAS will be a secondary analysis set for selected efficacy analyses.

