CT scans of chest, abdomen and pelvis ^{a, b}	X	X	X ^c
Bone marrow aspirate and/or biopsy ^d	X	X	
Focused physical examination and assessment of B symptoms	X	X	X
Response Assessment ^e	X	X	X

- a. CT scans of the chest, abdomen and pelvis are required for all subjects to document measurable disease at Screening and will be performed within 7 days prior to initiating the next cycle of study treatment (i.e. Day -7 to Day 1) of Cycles 3, 5, 7, 10 and at every fourth cycle thereafter (Cycle 14, 18, 22, etc.) while on-treatment with IPI-145. Other scans may be performed (e.g. head/neck CT) if clinically indicated or to evaluate a site of known disease. Copies of all scans will be sent for independent review of response assessment.
- b. 18-FDG PET/CT scan or MRI may be substituted if clinically indicated, but the modality chosen to evaluate each individual subject should be the same throughout the duration of the study. The frequency provided is the minimum required for study participation.
- c. Scans will be performed at the EoT if the subject is discontinued for reasons other than radiologic disease progression and a previous assessment has not been performed within 30 days of the EoT visit.
- d. Bone marrow biopsy and/or bone marrow aspirate required only for subjects who otherwise meet the criteria for a CR unless the subject had an adequate bone marrow biopsy at Screening that was negative for lymphoma or unless the subject had previously undergone a bone marrow procedure confirming the CR. If bone marrow aspirate and/or bone marrow biopsy is performed, bone marrow biopsies and/or aspirate samples (along with corresponding pathology report, if available) should be sent for biomarker analysis if available.
- e. Response assessment is determined using information from objective measurements of available CT scan, focused physical exam, bone marrow biopsy as relevant, and assessment of B symptoms.

Table 4: Long-term Follow-up Assessments for IPI-145 Monotherapy

	Disease follow-up ^a		Survival Follow-up ^c
	≤ 12 months from 1st Dose of IPI-145 Every 12 weeks	>12 months from 1st Dose of IPI-145 Every 16 weeks	
Response assessment ^b	X		
Survival			X

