CR	Disappearance of all evidence of disease	a) FDG-avid or PET positive prior to therapy: mass of any size permitted if PET negative b) Variable FDG-avid or PET negative prior to therapy: regression to normal size on CT	Not palpable, nodules disappeared	Infiltrate cleared on repeat biopsy; if indeterminate by morphology, immunochemistry should be negative
PR	Regression of measurable disease and no new sites	≥50% decrease in SPD of up to 6 largest dominant masses; no increase in size of other nodes a) FDG-avid or PET positive prior to therapy: one or more PET positive at previously involved site b) Variable FDG-avid or PET negative: regression on CT	≥50% decrease in SPD of nodules (for single nodule in greatest transverse diameter); no increase in size of liver and spleen	Irrelevant if positive prior to therapy; cell type should be specified
SD	Failure to attain CR/PR or PD	a) FDG-avid or PET positive prior to therapy: PET positive at prior sites of disease and no new sites on CT or PET b) Variable FDG-avid or PET negative; no change in size of previous lesions on CT		
Relapsed disease or PD	Any new lesion or increase by ≥50% of previously involved sites from nadir	Appearance of new lesion(s) >1.5 cm in any axis, ≥50% increase in SPD from nadir of more than one node, or ≥50% increase in longest diameter of a previously identified node >1 cm in short axis Lesions PET positive if FDG-avid lymphoma or PET positive prior to therapy	>50% increase from nadir in the SPD of any previous lesions	New or recurrent involvement

Abbreviations: CR, complete remission; FDG, [¹⁸F] fluorodeoxyglucose; PET, positron emission tomography, CT; computed tomography; PR, partial remission; SPD, sum of the product of the diameters; SD, Stable disease; PD progressive disease.

Adverse events, including SAEs, associated with any disease assessment must be collected per [Section 8.2.1](#).

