9.3 ANALYSIS SETS

The Full Analysis Set (FAS) will include all subjects who were treated with at least one dose of IPI-145. The FAS will be the primary analysis set for all efficacy and safety analyses.

The Evaluable Analysis Set (EAS) will include all subjects who had no major protocol violations and who remained in the treatment phase of the study for at least 8 weeks with an adequate baseline tumor assessment and at least 1 adequate post baseline tumor assessment. Subjects with documented disease progression before 8 weeks of treatment should be considered as “early progression” subjects and, therefore, should be considered evaluable. The EAS will be a secondary analysis set for selected efficacy analyses.

Major protocol violations include failure to satisfy key entry criteria, or taking other anticancer therapies or other prohibited medications during the treatment phase of the study that could seriously confound the effects of the study treatment.

For each of the above two analysis sets, subsets defined by disease subtypes will be identified so that efficacy analyses for disease subtypes can be performed.

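### SAP 4.2 waives the post-baseline assessment for death from progression but has no matching waiver in its 8-week criterion, so a death from progression before week 8 without IWG-documented PD still leaves the evaluable set

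*SAP*

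**What the plan says.** SAP 4.2 opens with "The Evaluable Analysis Set (EAS) will include all subjects who meet the following criteria", so the criteria apply jointly. Two of them matter here.

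- First criterion: "Remain in the treatment phase of the study for at least 8 weeks or have a documented disease progression per revised IWG criteria before 8" (counted in weeks). Death is not mentioned.
- Third criterion: "Have at least 1 adequate post baseline tumor assessment unless death due to disease progression".

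Protocol 9.3 has the same 8-week rule and an allowance for early progressors: "Subjects with documented disease progression before 8 weeks of treatment should be considered as “early progression” subjects and, therefore, should be considered evaluable". It requires an adequate post-baseline assessment and has no waiver for death. The waiver appears only in the SAP.

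Protocol Table 3, footnote a, schedules on-treatment CT scans "within 7 days prior to initiating the next cycle of study treatment (i.e. Day -7 to Day 1) of Cycles 3, 5, 7, 10"; later scans follow at four-cycle intervals. Protocol Table 8 defines progression by lesion and marrow findings ("Any new lesion or increase by ≥50% of previously involved sites from nadir") and does not list death.

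The EAS is a secondary set, used alongside the primary FAS for ORR (SAP 7.2.1.1), PFS (7.2.2.1) and OS (7.2.2.3), among others.

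**The concern.** The waiver in the third criterion appears intended to keep subjects who died of lymphoma before anyone could assess them. Most such deaths would be expected around or before the first scheduled scan, which nearly coincides with the 8-week mark. The first criterion then removes the same subjects, unless progression was documented in some other way.

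The subjects lost are treatment failures, so the effect runs in one direction: the EAS response rate can only rise, and early PFS and OS events can only be lost. There is also a practical risk. One programmer may apply the criteria literally and another may follow the apparent purpose of the waiver, which would give two different evaluable sets in an open-label trial.

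**Working it through.** **Design figures.** The documents state no EAS size or EAS response rate to reproduce. The FAS design does reproduce: with n = 120 and a null of 30%, the smallest significant count is 47 responders (exact one-sided alpha 0.0200). Power at 45% is 0.916, or 0.910 if the futility stop at 7 or fewer of 30 is obeyed. Both agree with the stated >90%.

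**Timing.** With 28-day cycles, Cycle 3 Day 1 is study day 2 × 28 + 1 = 57. The window opens 7 days earlier, on day 50. Eight weeks is 56 days. The first scheduled scan and the 8-week threshold therefore nearly coincide.

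**Tracing a subject through SAP 4.2.** Take a subject with an adequate baseline and no major deviation who dies of lymphoma before week 8 with no post-baseline assessment.

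1. Third criterion: met, through the waiver.
2. First criterion, 8-week limb: not met.
3. First criterion, documented-progression limb: not met, because no IWG finding was recorded and Table 8 does not treat death as progression.
4. Result: excluded.

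The same holds for a subject taken off treatment at week 5 for clinical decline who dies later without a scan, because SAP 7.1.6 ends time on treatment phase at the decision to discontinue.

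**Effect on ORR.** Under SAP 5.1 such a subject has a best response of unknown. Under SAP 7.2.1.1 the denominator is everyone in the analysis set, so the subject counts as a non-responder wherever included. With R responders of 120, k such exclusions and no other exclusions, EAS ORR = R/(120 − k). The value of k is assumed.

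| k | R = 54 (FAS 45.0%) | R = 36 (FAS 30.0%) |
|---|---|---|
| 2 | 54/118 = 45.8% | 36/118 = 30.5% |
| 4 | 54/116 = 46.6% | 36/116 = 31.0% |
| 6 | 54/114 = 47.4% | 36/114 = 31.6% |

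That is roughly 0.3 to 0.4 percentage points per excluded subject.

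**At the decision boundary.** SAP 7.2.1.1 applies its analyses to both sets. With 46 responders, 46/120 gives exact one-sided p = 0.0312 in the FAS. With k = 2, 46/118 gives p = 0.0231 in the EAS. The two sets would then fall on opposite sides of 0.025.

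**Time-to-event endpoints.** SAP Table 2 does not censor a subject who dies before the first post-baseline assessment, so in the FAS that death is a PFS event and an OS event. In the EAS both disappear. DOR covers responders only (SAP 7.2.2.2), so these subjects never enter it.

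**The case against.** Four stronger readings are tempting, and the documents do not support them.

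- *The fastest progressors as a group leave the EAS.* They do not. Early progression documented by IWG criteria is expressly kept. It can be documented on an end-of-treatment or unscheduled scan, or through examination or marrow findings, which Protocol Table 3 footnote e includes in response assessment.
- *The two criteria flatly contradict each other.* They can both be met. The waiver still works for a subject who stays 8 weeks or more without an adequate scan, including one whose Cycle 3 scan was inadequate, and for one whose early progression was documented without an adequate scan.
- *The SAP defeats the protocol's intent.* Protocol 9.3 protects only documented early progression and has no death waiver, so the SAP is the more inclusive text here. The argument for repair rests on the SAP's own waiver.
- *The main result is biased.* The FAS is primary and keeps these subjects as non-responders and as PFS and OS events.

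The size can also fairly be challenged. No document counts early lymphoma deaths. In the Phase 1 data in Protocol 1.5, only 2 of 29 evaluable iNHL subjects had progression as best response, and Protocol 1.3.3.2 gives a median of 8.5 cycles for the 32 iNHL subjects. This is weak reassurance, because the 29 are already restricted to evaluable subjects and the population may differ. Still, nothing points to many such deaths. A shift from 45.0% to 45.8% is small beside the exact 95% interval for 54/120, which is 35.9% to 54.3%. The set sizes (SAP 7.1.1) and the death tables and listings (SAP 7.3.1) will show part of the gap.

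These points limit the finding to a narrow group and a secondary set. They do not supply the waiver missing from the first criterion, and they do not change the direction of the effect.

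**Conclusion.** The point holds in a limited form. As written, SAP 4.2 excludes subjects who die of progression after less than 8 weeks in the treatment phase without IWG-documented progression, although its third criterion excuses those same subjects from an assessment. Given the scan calendar, the waiver is left with little effect.

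The direction is certain: any such exclusion raises the EAS ORR when there is at least one responder, and removes a PFS and an OS event. The size is not known. The shift of 0.8 to 2.4 percentage points at 54 responders rests on an assumed 2 to 6 deaths and on no other exclusions. How many subjects fall through also depends on whose assessment counts as documented, which SAP 4.2 does not say; a broad investigator reading would shrink the group. Severity is minor.

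**What to change.** In SAP 4.2, keep the two existing alternatives in the first criterion and add a third: *or discontinue before 8 weeks and die due to disease progression*. Death on treatment is covered, since Protocol 4.4 lists it as a reason for withdrawal from treatment. In the same place, state whether documented progression means IRC or investigator assessment. It would also help to report the number excluded under each criterion.

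No further rule is needed for ORR: SAP 5.1 and 7.2.1.1 already make these subjects non-responders once they are in the set.

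The cost is one clause and one clarification, with no new data collection. The EAS ORR becomes slightly less favourable. The EAS also becomes a little wider than Protocol 9.3 describes, so the change should be recorded in SAP section 8.
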